2.3. Benefit/Risk Assessment

No human studies have been conducted to date evaluating PF-07209960, as this is the FIH study. For selected disease indications where participants do not have access to curative treatment options, the benefit/risk relationship has been carefully considered in the planning of this trial based on pre-clinical, toxicology studies and safety profiles of PF-07209960.

Safety findings with PF-07209960 that were observed in the nonclinical studies include: fever, diarrhea, thrombocytopenia and immune cell infiltration of organs. During this Phase 1 study, clinical assessments will include frequent safety monitoring. The participants will be monitored during and following their first dose with a 72-hour inpatient hospitalization period. This will be implemented throughout dose escalation and length of inpatient hospitalization will be re-assessed based on safety data prior to starting dose expansion cohorts.

More detailed information about the known and expected benefits and risks and reasonably expected AEs of PF-07209960 may be found in the IB, which is the SRSD for this study.

2.3.1. Risk Assessment

Potential Risk of Clinical Significance	Summary of Data/Rationale for Risk	Mitigation Strategy
Study Intervention(s) PF-07209960		
CRS	
The potential risks are based on pre-clinical toxicology data for PF-07209960 and prior clinical experience with the IL-15 and anti-PD-1 drug classes.
	
CRS: Participants will be closely monitored with 72 hour inpatient hospitalization on first dose at least for all in dose escalation. Guidelines for the management of CRS (Appendix 9) and irAEs (Appendix 14) have been incorporated.
 
If the IV route is evaluated, there will be a minimum 72-hour interval between the first dose administered to each of the initial 2 participants enrolled at a new dose level to allow the detection of CRS. For C1D15 PF-07209960 IV administration, participants should remain at the investigational site for observation for at least 8-hours post dose.

Thrombocytopenia including bleeding		
Thrombocytopenia: Participants must have both adequate hematological functions (including platelet counts) and coagulation functions to be eligible to participate in this study. Hematological and coagulation functions will be performed throughout. Anti-coagulants must be held for low platelet counts, and anti-platelet medications must be held for at least the first week of treatment.

Abnormal liver function, abnormal kidney function		
Abnormal liver and kidney functions: Participants must have adequate liver function and kidney functions to be eligible to participate in this study. Liver and kidney function tests will be performed throughout the study.

Potential Risk of Clinical Significance	Summary of Data/Rationale for Risk	Mitigation Strategy
Study Intervention(s) PF-07209960		
irAEs including myocarditis		irAEs including myocarditis: Participants must have a LVEF: \geq 50% by echocardiogram or MUGA to be eligible. CCI [REDACTED]
Male infertility due to low sperm count		Male participants should be counseled on option of fertility preservation.
SC injection site reaction.	There is a risk associated with any SC injection.	ISRs will be monitored at each injection.
Study Procedures		
De novo (fresh) tumor biopsy 
 • stinging pain from injection of local anesthetic; • pain or discomfort from the biopsy procedure; • discomfort from lying still for an extended time; • bleeding, swelling, scanning, soreness, or bruising at the biopsy site; • infection of wound contamination of cancer cells to unaffected tissue when removing biopsy needle.	There is a risk associated with any tumor biopsy.	Local anesthetic will be administered. Sterile techniques will be used. Procedures will be performed by qualified medical practitioners. Mandatory fresh biopsies will be limited to dose expansion (Part 2). Participants should not be subjected to a significant risk procedure to obtain the biopsies (ie, the absolute risk of mortality or major morbidity in the participant's clinical setting and at the institution completing the procedure should be $<2\%$).

2.3.2. Benefit Assessment

There is a potential benefit of the participant's tumors shrinking due to the study treatment, which could translate into an improvement in cancer-related symptoms or prolonged PFS or OS. The participant would also be contributing to the development of a novel therapy in an area of unmet need. Medical evaluations and assessments on the study will allow for better monitoring of the participants and recognition of AEs whether related to treatment or not.

2.3.3. Overall Benefit/Risk Conclusion

Taking into account the measures taken to minimize risk to participants in this study, the potential risks identified in association with PF-07209960 are justified by the anticipated benefits that may be afforded to participants with advanced or metastatic solid tumors.

3. OBJECTIVES AND ENDPOINTS

PART 1 DOSE ESCALATION	
Objectives	Endpoints
Primary:	Primary:

 To assess safety and tolerability at increasing dose levels of PF-07209960 in participants with select locally advanced/metastatic solid tumors in order to estimate the MTD and select the RP2D/schedule. 	
 First cycle DLTs. AEs as characterized by type, frequency, severity (as graded by NCI CTCAE version 5.0; for CRS as graded by ASTCT criteria), timing, seriousness, and relationship to study therapy. Laboratory abnormalities as characterized by type, frequency, severity (as graded by NCI CTCAE version 5.0), and timing.

 To characterize the single and multiple dose PK of PF-07209960. 	
 Single dose: Cmax, Tmax, AUCtau, If data permits, AUCinr, CL/F, t1/2; Multiple Dose: Cma."<Ss, Tmax,ss, AUCtau,ss, If data permits, CLss/F, t1/2,ss, and Rae; Ctrou at selected time points. Incidence, titers and endogenous IL-15 cross-reactivity of ADA and NAb against PF-07209960.

 To evaluate the immunogenicity of PF-07209960. To evaluate preliminary anti-tumor activity. 	
 ORR, DCR as assessed using the RECIST version 1.1. Time-to-event endpoints: DOR, PFS, and TTP by RECIST version 1.1
Exploratory:	Exploratory:
CC CCI	
I	
I	

PART 1 DOSE ESCALATION		
	Objectives	Endpoints
I	CC1	
I		
I		

PART 2 DOSE EXPANSION	
Objectives	Endpoints
Primary:	Primary:

 To confirm safety and tolerability of PF-07209960 at the RP2D in participants with selected tumor types. To evaluate preliminary evidence of anti-tumor activity of PF-07209960 in participants with selected tumor types. 	
 AEs as characterized by type, frequency, severity (as graded by NCI CTCAE version 5.0; for CRS as graded by ASTCT criteria), timing, seriousness, and relationship to study therapy. Laboratory abnormalities as characterized by type, frequency, severity (as graded by NCI CTCAE version 5.0), and timing. ORR as determined by RECIST version 1.1.
Secondary :	Secondary :

 To further evaluate the PK of PF-07209960 at the RP2D. To evaluate the immunogenicity of PF-07209960. To evaluate the effect of PF-07209960 on immune cells in tumor biopsies. To evaluate preliminary anti-tumor activity through time to event endpoints. To assess overall survival of participants treated with PF-07209960. 	
 Single dose: Cmax, T_{max}, AUC_{0-∞}. If data permits, AUC_{0-t}, CL/F, t_{1/2}; Multiple Dose: Cmax,ss, T_{max},ss, AUC_{0-∞},ss. If data permits, CL_{ss/F}, t_{1/2,ss}, and Rae; Through at selected time points. Incidence, titers and endogenous IL-15 cross-reactivity of ADA and NAb against PF-07209960. Intra-tumor T cells (such as by CDS IHC) in on-treatment versus baseline tumor biopsy samples. DCR, DOR, PFS, and TTP by RECIST version 1.1 Overall survival
Exploratory:	Exploratory:
I	
I	
I	

PART 2 DOSE EXPANSION		
	Objectives	Endpoints
I	CCI	
I		
I		

4. STUDY DESIGN

4.1. Overall Design

This is a Phase 1, open-label, multi-center, multiple-dose, dose escalation, safety, PK and PD study of PF-07209960 in cohorts of adult participants with selected locally advanced or metastatic solid tumors (anti-PD-1/PD-L1 resistant- NSCLC, SCCHN, RCC, UC; or anti-PD-1 naïve OvCa and MSS CRC) for whom no standard therapy is available or in the opinion of the participant and their treating physician, that standard therapy would not be appropriate, or who have refused standard therapy.

The study contains 2 parts, single agent dose escalation (Part 1) followed by a dose expansion at RP2D (Part 2). Following the determination of the RP2D based on sequential dose escalation cohorts with single agent PF-07209960 in Part 1, the respective expansion cohorts in Part 2 will commence.

The Part 2 dose expansion phase will consist of up to 5 cohorts, which will evaluate safety and anti-tumor activity of PF-07209960 at the RP2D determined in Part 1. Opening of cohorts in Part 2 will initially include tumor type(s) and setting(s) deemed more likely to demonstrate anti-tumor activity based on data from Part 1. At this time, Part 2 expansion cohorts in NSCLC, RCC and UC have been chosen due to their responsiveness to immunotherapy agents, and only if preliminary anti-tumor activity is seen with OvCa and MSS CRC in Part 1 or in NSCLC, RCC, and UC in Part 2, OvCa and MSS CRC expansion cohorts would be considered for enrollment. Other indications for Part 2 could be re-prioritized based on emerging data from Part 1. Dose escalation and expansions combining PF-07209960 with anti-PD-L1 or other agents may be added through protocol amendment based on emerging data. The overall study design is depicted in the schema (Section 1.2).

BLRM guided by EWOC principle will be used to guide dose escalation process and determine the MTD/RP2D (Part 1). Successive cohorts of participants in Part 1 will receive escalating doses of PF-07209960 as a SC injection every 2 weeks in 28-day cycles; the SC route has the potential to reduce the Cmax which is believed to be associated with CRS and

inflammatory responses, a common AE for agents that stimulate T cells. If excessive ISR or unexpected low exposure is encountered with SC dosing, an alternative IV infusion Q2W administration may be explored. The IV dose escalation/finding would begin at a starting dose based on the available emerging clinical data (including safety/tolerability, PK, PD) from the dose escalation cohorts with SC Q2W administration. The first and second participant in each dose level must be enrolled >72 hours apart.

Approximately 14-22 participants are expected to be enrolled into Part 1 and approximately 60-90 participants will initially enroll into the first three cohorts in Part 2. Based on emerging data, with the option to further enroll approximately 40-60 participants in an additional two cohorts in Part 2. Clinical response will be continuously monitored in each expansion cohort and if no clinical benefit is observed enrollment may be stopped in the respective cohort.

All participants will complete up to 28 days of screening prior to enrollment.

Eligible participants will receive PF-07209960 as a SC injection or IV infusion on Days 1 and 15 as described in [Section 4.3.1](#). A cycle will consist of 28 days and treatment with study intervention will continue until progression of disease, unacceptable toxicity, participant refusal, or whichever is earliest, unless the investigator and medical monitor agree to treatment beyond disease progression based on individual benefit/risk assessments or agree to discontinue treatment or the study is terminated. Participants will be allowed to stay on treatment despite initial radiological disease progression per RECIST version 1.1 ([Eisenhauer et al, 2009](#)) if all of the following criteria are met:

- The investigator feels that it is in the participant's best interest and has discussed with the medical monitor;
- There is absence of symptoms and signs indicating clinically significant progression of disease;
- There is no decline in performance status;
- There is absence of symptomatic rapid disease progression requiring urgent medical intervention (eg, symptomatic pleural effusion, spinal cord compression);
- It is documented that the participant consents to continued participation in the study even after being informed of all available approved therapies and their potential clinical benefit that they may be forgoing in order to continue the study intervention.

Participants experiencing toxicity including a DLT may be managed with dose modification or discontinuation from treatment. The proposed doses, schedule(s) and PK time points may be reconsidered and amended during the study based on the emerging safety and PK data.

Assessment of late toxicities will also be completed after the DLT observation period of 28 days after C1D1 for all participants. Once a dose level has been declared safe following the post DLT observation window, participants at lower dose levels who have completed the DLT observation period may escalate to the next higher dose level, if criteria outlined in [Section 4.3.2.1](#), Criteria for Intraparticipant Dose Escalation, have been met.

Participants continuing to experience AEs following discontinuation of treatment will continue to be followed at least every 4 weeks until resolution or determination, in the clinical judgment of the investigator, that no further improvement is expected. Participant will continue a 1-month follow-up visit after the last dose for AE and SAE follow-up if necessary. After the 1-month follow-up, participants will be contacted by telephone every 8 weeks (± 7 days) to obtain information on subsequent anticancer treatment, any AEs/SAEs experienced up to 90 days after the last dose, and survival status until the end of the study ([Section 4.4](#)). If the unresolved AE is considered by the investigator as possibly related to or associated with ADA formation, the participant will be asked to return to the clinic for ADA assessment at approximately 3 month intervals (if feasible given the underlying disease) until the AE or its sequelae return to baseline or stabilize at a level acceptable to the investigator and sponsor, until the last follow-up of the AE.

The biomarker studies will be used to help understand the *in vivo* mechanism of action of the agent(s) studied as well as potential mechanisms of resistance. The studies may help in the future development of PF-07209960 as a single agent, or in combination with other compounds, and may provide information on tumor sub-types that may respond to the study intervention.

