1.3. Schedule of Activities

The SoA table provides an overview of the protocol visits and procedures. Refer to the **STUDY ASSESSMENTS AND PROCEDURES** section of the protocol for detailed information on each assessment required for compliance with the protocol.

The investigator may schedule visits (unplanned visits) in addition to those listed in the SoA table, in order to conduct evaluations or assessments required to protect the well-being of the participant.

	Screening	Cycle 1 (28 days)-A Cycle 2 (28 days) - B Cycle >3 (28 days) - C												Notes
		1 A	1 B/C	2 A	3 A	4 A	8 A	15 A/B/C	16 B	17 B	18 B	22 A/B		
Days	Up to 28 days prior to CIDI													
Visit Window		-72 h1's	±2 davs	±4 hrs	±4 h.-s	±4 hrs	±1 day	±2 davs	±4 h.-s	±4 h1's	±24 h.-s	±24 hrs		
Informed consent and registration	A	A												
 Info,med consent must be obtained prior to undergoing any study-specific procedures. Participant enrollment number and dose level allocation assigned by Pfizer Inc.
Medical History	A													
 Includes tumor history and other medical history.
Physical Examination														
Complete Physical Exam	A	A												
 Include height only at screen (not needed at CIDI). Include weight at screening..
Brief Physical Exam			B/C	A	A	A	A	A/B/C					A/B	
 Include weight D1 of each cycle only. Height not needed. Daily while hospitalized.
ECOG Performance Status	A	A	B/C					A/B/C						
Vital Signs	A	A	B/C	A	A	A	A	A/B/C						
 Measure vitals prior to the PF-07209960 treatment.

	Screening	Cycle 1 (28 days)-A Cycle 2 (28 days) - B Cycle >3 (28 days) - C												Notes	
		Days	Up to 28 days prior to CIDI	1 A	1 B/C	2 A	3 A	4 A	8 A	15 A/B/C	16 B	17 B	18 B	22 A/B	
Visit Window			-72 h1's	±2 davs	±4 hrs	±4 h.-s	±4 hrs	±1 day	±2 davs	±4 h.-s	±4 h1's	±4 h.-s	±24 hrs		

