4.3.1.2. Alternative IV Dosing

Based on the available emerging clinical data (including safety/tolerability, PK, PD) from the dose escalation cohorts with SC Q2W administration, IV infusion Q2W administration may be explored in successive dose cohorts. If IV administration is introduced, PF-07209960 will be administered over 1 hour (± 10 minutes) without adjustment for body size at every cycle as indicated in the IP manual. In case of change of the dosing regimen, DLT data accumulated during the dose escalation with the previously explored regimen may be used to inform a prior distribution for new BLRM parameters.

If the IV route is evaluated, there will also be a minimum 72-hour interval between the first dose administered to each of the initial 2 participants (ie, participants contributing to initial DLT evaluation) enrolled at a new dose level to allow the detection of possible infusion

reactions or possible CRS. The participants will be monitored during and following their first dose with at least a 72-hour inpatient hospitalization period. This will be implemented throughout dose escalation and length of inpatient hospitalization will be re-assessed based on safety data prior to starting dose expansion cohorts. Participants should remain at the investigational site for observation for at least 1-hour post dose for all treatment visits after C1D1. Additional inpatient observation for subsequent cycles beyond C1D1 may be considered based on the investigator's discretion and should be discussed with sponsor.

As described in [Section 4.3.1.1](#), the SC starting dose is 1.1 mg SC (rounded to 1 mg). The corresponding IV [CCI](#) the projected exposure associated with the IV dose lower than the projected exposure associated with SC dosing (Table 1).

Table 1. Projected Exposure After SC and IV Dosing

Human Dose	Cmax (μ g/ml)	AUC (μ g*hr/mL)
CCI		

The C_{max} after IV dosing was calculated by the dose divided by the human plasma volume (2.8 L); the C_{max} and AUC in human after SC, and the AUC after IV dosing were derived from the projected human PK profile extrapolated from monkey PK.

The following scenarios would be used to determine the IV starting dose:

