5. STUDY POPULATION

This study can fulfill its objectives only if appropriate participants are enrolled. The following eligibility criteria are designed to select participants for whom participation in the study is considered appropriate. All relevant medical and nonmedical conditions should be taken into consideration when deciding whether a particular participant is suitable for this protocol.

Prospective approval of protocol deviations to recruitment and enrollment criteria, also known as protocol waivers or exemptions, is not permitted.

Pfizer will review eligibility criteria verified by the investigator or qualified designee to confirm that participants meet study eligibility criteria before they are enrolled into the study. The enrollment approval process will be initiated for a participant after an informed consent document has been signed and the investigator or qualified designee has assessed the participant as eligible. The enrollment approval will be based on review of CRF/system data.

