6.3. Measures to Minimize Bias: Randomization and Blinding

6.3.1. Allocation to Study Intervention

Part 1: Dose Escalation

Dose level allocation will be performed by the sponsor after participants have given their written informed consent and have completed the necessary baseline assessments. The site staff will fax/e-mail a complete Registration Form to the designated sponsor study team member or designee. The sponsor will assign a participant identification number and supply this number to the site. The participant identification number will be used on all study-related documentation at the site.

No participant will receive study intervention until the investigator or designee has received the following information in writing from the sponsor:

- Confirmation of the participant's enrolment;
- Specification of the dose level for that participant and;
- Permission to proceed with dosing the participant.

Study intervention will be dispensed at the study visits summarized in the [SoA](#).

Returned study intervention must not be redispensed to the participant.

Part 2: Dose Expansion

If IRT will be utilized for Dose Expansion, allocation of participants to treatment groups will proceed through the use of an IRT system (IWR). If IRT will not be used, the Dose Expansion will follow the dose level allocation as indicated in the above Part 1, Dose Escalation section. The site personnel (study coordinator or specified designee) will be required to have an active or valid account and password with the IRT system, enter or select information including but not limited to the users' ID and password, protocol number, specific protocol entrance criteria indicated in the system and the participant number. The site personnel will then be provided with, at a minimum, a treatment assignment, randomization number, and DU or container number when study intervention is being supplied via the IRT system. The IRT system will provide a confirmation report containing the participant number, randomization number, and DU or container number assigned. The confirmation report must be stored in the site's files.

Study intervention will be dispensed at the study visits as summarized in the [SoA](#).

Returned study intervention must not be redispensed to the participants.

The study-specific IRT reference manual will provide the contact information and further details on the use of the IRT system.

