9.3. Analysis Sets

1. Full analysis set.

The full analysis set includes all enrolled participants.

"Enrolled" means a participant's, or their legally authorized representative's, agreement to participate in a clinical study following completion of the informed consent process. Potential participants who are screened for the purpose of determining eligibility for the study, but do not participate in the study, are not considered enrolled, unless otherwise specified by the protocol.

2. Safety analysis set.

The safety analysis set includes all enrolled participants who receive at least one dose of study intervention. Unless otherwise specified, the safety analysis set will be the default analysis set used for all analyses.

3. Per protocol analysis set (evaluable for MTD).

The per protocol analysis set includes all enrolled and evaluable participants who had at least one dose of study treatment and either experienced DLT or do not have major treatment deviations during the DLT observation period.

4. mITT Population.

The mITT is the analysis population that will follow the ITT principle and include participants receiving at least 1 dose of study medication with baseline assessment and at least 1 post baseline assessment, disease progression, or death before the first tumor assessment. The mITT population may be used for interim analysis and conference presentations when the study is still ongoing.

5. PK analysis sets.

The PK parameter analysis population is defined as all enrolled participants treated who do not have protocol deviations influencing PK assessment, and have sufficient information to estimate at least 1 of the PK parameters of interest.

The PK concentration population is defined as all enrolled participants who are treated and have at least 1 postdose analyte concentration.

6. Response Evaluable Set.

The response evaluable population will include all participants who received at least one dose of study treatment and had baseline disease assessment and at least one post baseline disease assessment.

7. PD/Biomarker analysis set(s).

The PD/Biomarker analysis population is defined as all enrolled participants with at least 1 of the PD/Biomarkers evaluated at pre and/or post dose.

8. Immunogenicity analysis set.

The immunogenicity analysis set includes all enrolled participants who receive at least one dose of study treatment and have at least one sample tested for ADA.

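### The 72-hour stagger that covers SC dosing is counted between enrolments, so as worded it does not guarantee 72 hours between the first two SC doses at a dose level

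*Protocol*

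**What the plan says.** **The stagger for all dose levels.** Protocol Section 4.1 states: "The first and second participant in each dose level must be enrolled >72 hours apart". The synopsis (Overall Design) and SAP 2.2 carry the same sentence, each shortly after saying that dosing may be SC or IV. The clock runs between enrolments.

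**The interval between doses.** In the readable text this appears twice, each time conditional on IV. The CRS row of Section 2.3.1 reads: "If the IV route is evaluated, there will be a minimum 72-hour interval between the first dose". Section 4.3.1.2 reads: "If the IV route is evaluated, there will also be a minimum 72-hour interval between the first". Section 2.3.1 gives detection of CRS as the purpose; Section 4.3.1.2 adds infusion reactions.

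**Enrolment and dosing.** Section 4.1 places enrolment after screening: "All participants will complete up to 28 days of screening prior to enrollment". Section 5 describes a sponsor approval step: "The enrollment approval process will be initiated for a participant after an informed consent document has been signed". Section 6.3.1 lists confirmation of enrolment and "Permission to proceed with dosing the participant" as separate items that the site must hold in writing before dosing. No time interval is attached to either.

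**Observation after dosing.** Every Part 1 participant stays in hospital for 72 hours after the first dose, whichever route is used (synopsis; Section 8.2.9).

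**The concern.** A stagger protects participant 2 by letting a reaction in participant 1 show itself first, so the interval that matters runs from dose to dose. A rule counted on enrolment delivers that interval only if participant 1 does not wait longer for the first dose than participant 2.

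The SC cohorts are the first human exposures. Section 6.5.11.4 says CRS appears several hours or days after administration, and Section 2.2.3 reports that the toxicity findings in animals were similar by SC and IV. The 72-hour inpatient stay applies to both routes, so the protocol treats those hours as relevant for SC as well. If participant 2 is dosed inside that window, a delayed reaction in participant 1 may not yet be visible. Unequal waits are plausible in a multicentre study in which each first dose needs a hospital admission.

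**Working it through.** This is a timing rule, so there is no sample-size or error-rate figure to reproduce. The plan's own figure is the stagger of more than 72 hours between enrolments.

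**Inputs**
- Enrolment gap G = E2 - E1, required to exceed 72 h (synopsis; Section 4.1; SAP 2.2).
- Enrolment is taken as sponsor approval after screening (Sections 4.1, 5 and 6.3.1).
- L1 and L2 are the hours from enrolment to first dose for participants 1 and 2. The documents give no values, so these are assumptions. The largest value used, 72 h, is the visit window before Cycle 1 Day 1 in the Schedule of Activities, where the Day 1 column includes the consent and registration row. The window does not say that enrolment happens that early; it serves only as an outer case.

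**Formula**

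First doses fall at D1 = E1 + L1 and D2 = E2 + L2. Therefore

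D2 - D1 = G + L2 - L1 > 72 + (L2 - L1).

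**Gap guaranteed at the minimum enrolment gap**

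| L1 (h) | L2 (h) | 72 + L2 - L1 | Guaranteed gap between SC first doses |
|---|---|---|---|
| 0 | 0 | 72 | >72 h |
| 48 | 48 | 72 | >72 h |
| 24 | 72 | 120 | >120 h |
| 48 | 24 | 48 | >48 h |
| 72 | 24 | 24 | >24 h |
| 72 | 0 | 0 | order only |

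Equal lags, or a longer wait for participant 2, keep the gap above 72 h. Only a longer wait for participant 1 shortens it.

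**When the interval is lost for a given enrolment gap**

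D2 - D1 < 72 exactly when L1 - L2 > G - 72.

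| Actual G (h) | Participant 1's extra wait must exceed (h) |
|---|---|
| 73 | 1 |
| 96 | 24 |
| 120 | 48 |
| 144 | 72 |
| 168 | 96 |

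A longer wait for participant 1 is therefore not enough by itself; it must use up the whole excess of G over 72 h.

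**Comparison.** For IV, the stated minimum is 72 h between first doses whatever the lags. With the same wording for SC, the SC minimum would also be 72 h whatever the lags.

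**The case against.** **Text that cannot be read.** Part of Section 4.3.1.1 is redacted, Section 4.3.2 breaks off in its dose table, and the text of Section 4.3.2.1 is lost from the public copy. An SC dose interval could stand there, and the word *also* in Section 4.3.1.2 suggests that one was intended. This stands. A reader might infer that the plan contains no SC dose interval at all; the documents do not support that. What can be said is that the synopsis, Section 4.1 and SAP 2.2 do not state one.

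**Screening time.** A reader might go further and count the lag from consent. Section 9.3 ties enrolment to "agreement to participate in a clinical study following completion of the informed consent process", and the Schedule of Activities says "consent must be obtained prior to undergoing any study-specific procedures", with screening lasting up to 28 days. On that reading the stagger could vanish or the order of dosing reverse. The operational text does not support this. Section 9.3 defines an analysis set, while Sections 4.1, 5 and 6.3.1 place enrolment after screening and sponsor approval. The 28-day case is not relied on.

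**A deliberate difference.** SC may lower the Cmax believed to drive CRS (Section 4.1), infusion reactions belong to IV, and another IL-15 agent given SC caused rashes without constitutional symptoms (Section 2.2.4). These points lower the likely harm. They do not explain why the SC clock starts at enrolment when the inpatient stay is the same for both routes.

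**Sponsor control.** The sponsor releases each Part 1 participant in writing, and safety issues go to it immediately (Sections 6.3.1 and 8). A signal already seen in participant 1 can therefore stop participant 2. That is a real safeguard, but it does not require anyone to wait for a signal that has not yet appeared. Nor would a 72-hour dose interval exclude every later CRS event.

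**Conclusion.** The point holds in a limited form. As worded in the synopsis, Section 4.1 and SAP 2.2, the stagger covering SC dosing fixes the interval between enrolments and leaves the interval between first doses dependent on scheduling. The SC interval falls below 72 h only when participant 1's wait exceeds participant 2's by more than G - 72 hours. At the minimum enrolment gap, lags of 48 h and 24 h guarantee only more than 48 h.

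This rests on three things: enrolment means approval after screening, the lags are assumed, and no SC dose interval stands in the unreadable text. A reader might infer that near-simultaneous dosing is to be expected. The documents do not support that: it would need participant 1 to wait the full 72-hour window, participant 2 to be dosed on enrolment, and the enrolment gap to sit at its minimum. Nothing suggests that participant 1 systematically waits longer. No endpoint or analysis changes. It is a safety rule tied to the wrong event, and correcting it is a cheap improvement.

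**What to change.** - In the synopsis, Section 4.1 and SAP 2.2, replace the enrolment wording with: *at least 72 hours must elapse between the first doses of the first and second participants at each new dose level, SC or IV.*
- In Section 2.3.1, make the interval in the CRS row apply to both routes.
- In Section 6.3.1, make the interval a condition of the sponsor's written permission to dose the second participant.
- If an SC dose interval already stands in Section 4.3.1.1, 4.3.2 or 4.3.2.1, cite it in these places so that all state the same rule.

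The cost is wording, plus a delay of at most a few days to the second participant's first dose at each dose level. The release step that would enforce the rule already exists.
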